5.3.7.2 Adverse event collection and reporting

AE Collection

The Investigator shall maintain and keep detailed records of all AEs in their patient files. The following must be collected and documented on the appropriate eCRF(s) by the Investigator:

- From signing the ICF onwards through the Residual Effect Period (REP), until individual patient's end of trial participation:
 - all AEs (serious and non-serious), Outcome events and all AESIs.
- After the individual patient's end of trial:

The Investigator does not need to actively monitor the patient for AEs, but must report relevant SAEs and relevant AESIs of which the Investigator may become aware of.

The REP (timeframe after last dose of trial medication when measurable drug levels or pharmacodynamic effects are still likely to be present) is defined as 7 days after the last trial medication application. All AEs which occurred through the treatment phase and throughout the REP will be considered as on treatment. Please also refer to [Section 7.3.4](#).

Events which occurred after the REP will be considered as post treatment events.

[figure not shown]

Figure 5.3.7.2: 1 Timelines for adverse event collection

AE reporting to the Sponsor/CRO and timelines

The Investigator must report all non-exempted SAEs, AESI and any non-serious AE relevant for the reported SAE, immediately (within 24 hours) on the BI SAE form. The same timeline applies if follow-up information becomes available.

For Japan only: All SAEs must be reported immediately to the head of the trial site.

Any protocol exempted event that occurs prior to randomisation and fulfils the criteria of an SAE will be reported immediately (within 24 hours) by the Investigator on the BI SAE form via fax immediately (within 24 hours) to the Sponsor's/CRO's unique entry point (country specific contact details will be provided in the ISF); **however, if the patient has been randomised, the exempted events will not be reported as SAEs to the sponsor and no causality assessment will be performed. These events will be entered only on the AE eCRF pages (within 24 hours). The investigator is also required to provide all defined supporting documentation.**

In specific occasions the Investigator could inform the Sponsor/CRO upfront via telephone. This does not replace the requirement to complete and fax the BI SAE form.

If any exempted event or any other adverse event (serious or non-serious) occurs, the investigator or attending physician has the responsibility and will take direct and appropriate action to provide care for the patient and to decide whether or not the trial medication should be discontinued.

An independent Data Monitoring Committee (DMC) will monitor the safety data in the trial on an ongoing basis. Reported SAEs occurring after randomisation that are protocol exempted events will be collected in the eCRFs and evaluated by the DMC. These events will not be collected on SAE forms for expedited review or reporting.

Proprietary confidential information © 2016 Boehringer Ingelheim International GmbH or one or more of its affiliated companies

Aggregate analysis of endpoint data to determine any potential benefit or risk and to ensure patient safety during the clinical trial will be performed on a regular basis by the DMC.

With receipt of any further information to these events, appropriate follow-up forms have to be provided. For follow-up information the same rules and timeline apply as for initial information.

Information required

For each AE, the Investigator should provide the information requested on the appropriate eCRF pages and the paper SAE form. The Investigator should determine the causal relationship to the trial medication.

The following should also be recorded as an (S)AE in the CRF and SAE form (if applicable):

- Worsening of the underlying disease or of other pre-existing conditions. Exemptions are specified in “Exemptions to SAE reporting” and must be adhered to as described in that chapter.
- Changes in vital signs, ECG, physical examination and laboratory test results, if they are judged clinically relevant by the Investigator. If such abnormalities already pre-exist prior trial inclusion they will be considered as baseline conditions.

All (S)AEs, including those persisting after individual patient’s end of trial must be followed up until they have resolved, have been sufficiently characterised, or no further information can be obtained.

For some types of AEs additional information will be collected in the CRF due to the nature of the event and mechanisms of action of the trial medication. These listed AEs are distinct from AESI:

- Hypoglycaemic event
- Genital infection
- Acute pyelonephritis
- Sepsis
- Urinary tract infection
- Bone fracture

Pregnancy

In rare cases pregnancy may occur in a clinical trial. Once a patient has been enrolled into this clinical trial and has taken trial medication, the Investigator must report immediately (within 24 hours) a potential drug exposure during pregnancy (DEDP) to the Sponsor’s/CRO’s unique entry point (country-specific contact details will be provided in the ISF). The Pregnancy Monitoring Form for Clinical Trials (Part A) should be used.

The outcome of the pregnancy associated with the drug exposure during pregnancy must be followed up and reported to the Sponsor’s/CRO’s unique entry point on the Pregnancy Monitoring Form for Clinical Trials (Part B).

The ISF will contain the Pregnancy Monitoring Form for Clinical Trials (Part A and B).

Proprietary confidential information © 2016 Boehringer Ingelheim International GmbH or one or more of its affiliated companies

As pregnancy itself is not to be reported as an AE, in the absence of an accompanying SAE and/or AESI, only the Pregnancy Monitoring Form for Clinical Trials and not the SAE form is to be completed. If there is an SAE and/or AESI associated with the pregnancy an SAE form must be completed in addition.

Exemptions to SAE reporting

A list of serious adverse events that commonly occur in the trial population or which are components of trial endpoints are exempted from expedited reporting. These events are known consequences of the underlying disease and it is not possible, based on a single case, to conclude that there is a reasonable possibility that the investigational drug caused these events. Pulmonary complications of heart failure are added to the exemption list, since patients with HF commonly experience such complications. Thus these events could be reported as pulmonary events, although the underlying aetiology was attributed to HF.

Regardless of relationship to trial medication, these events will not be reported by the Sponsor to regulatory agencies or ethics committees in an expedited manner.

These events include:

Cardiovascular (CV) related death. The CV related death also includes death due to undetermined cause, and death due to pulmonary events that may be secondary to complications of heart failure such as pulmonary oedema, pulmonary vascular disease secondary to heart disease.

HF hospitalisation

Non-fatal MI

Non-fatal stroke and Transient ischemic attack (TIA)

CV hospitalisation events

Pneumonia (fatal and non-fatal)

New or exacerbated COPD (fatal and non-fatal)

Based on the same conclusion that it is not possible to perform a causality assessment on these events based on a single case, the trial investigators are exempted from performing a causality assessment and reporting these serious adverse events on the SAE form to the Sponsor.

All such events will be collected systematically on the eCRF (within 24 hours) from the time of randomisation throughout follow up.

This reporting policy assumes global regulatory agency approval.

5.4 DRUG CONCENTRATION MEASUREMENTS AND PHARMACOKINETICS (SUBSTUDY)

5.4.1 Pharmacokinetic endpoints

The PK sampling will be done from a limited number of randomised patients (approximately 1650 patients) and at pre-selected sites only. The pre-dose blood samples will be collected at visit 4 to determine plasma empagliflozin trough concentrations. These samples will serve to determine steady state trough concentrations of empagliflozin.

Proprietary confidential information © 2016 Boehringer Ingelheim International GmbH or one or more of its affiliated companies

The date and exact clock time of trial medication intake the day before this visit will be recorded together with the date and exact clock time of drawing the trough pharmacokinetic sample.

5.4.2 Methods of sample collection

The time interval for blood sample collection relative to the most recent intake of trial medication should be between 22 and 26 h. For quantification of empagliflozin trough plasma concentrations, 3 mL of blood will be drawn from a forearm vein in an EDTA-anticoagulant blood drawing tube at each time-point. Details of sample handling and sample logistics can be found in the ISF (Central lab manual).

5.4.3 Analytical determinations

Empagliflozin concentrations in plasma samples will be determined by a validated HPLC MS/MS assay (high performance liquid chromatography, tandem mass spectrometry). In order to identify samples from patients taking placebo, the bioanalyst will be un-blinded so that samples from patients receiving placebo will not be analysed for empagliflozin.

5.5 ASSESSMENT OF BIOMARKERS

Samples for NT-proBNP will be collected at Visit 1 (Screening) to determine whether the patient is eligible for the trial. Further samples for NT-proBNP will be collected at later time points in the trial (see [Flow Chart](#)) to investigate a potential effect of the trial medication. Samples for NT-proBNP will be analysed at the Central Laboratory.

Samples for the determination of high-sensitivity cardiac troponin T will be collected at Visit 2 (Randomisation) and analysed at the Central Laboratory.

5.5.1 Biobanking (optional)

Participation in sampling for biobanking (including DNA) is voluntary and not a prerequisite for participation in the trial. Biobanking samples will be taken only after separate informed consent has been given in accordance with local ethical and regulatory requirements. Banked samples may be analysed in the future for scientific evaluations or to further, for example, the mechanistic understanding of drug effects and/or to identify genetic or other factors associated with response to therapy or the risk of adverse drug reactions.

Measures are in place to comply with the applicable rules for the collection, biobanking and future use of biological samples and clinical data, in particular.

- Sample and data usage has to be in accordance with the separate biobanking ICF.
- The BI-internal facilities storing biological samples from clinical trial participants as well as the external banking facility are qualified for the storage of biological samples collected in clinical trials
- An appropriate sample and data management system, incl. audit trail for clinical data and samples to identify and destroy such samples according to ICF is in place

Proprietary confidential information © 2016 Boehringer Ingelheim International GmbH or one or more of its affiliated companies

- A fit for the purpose documentation (biomarker proposal, analysis plan and report) ensures compliant usage
- A fit for purpose approach will be used for assay/equipment validation depending on the intended use of the biomarker data
- Samples and/or data may be transferred to third parties and other countries as specified in the biobanking ICF

5.5.1.1 Methods and timing of sample collection

Sampling will be performed at the time points specified in the Flow chart.

DNA banking

Approx. 8.5 mL blood will be drawn into a PAXgene Blood DNA Tube, preferably at Visit 2.

Plasma banking

Approx. 10 mL blood will be drawn into an EDTA blood collection tube.

Serum banking

Approx. 8.5mL blood will be drawn into a serum separation tube.

Urine banking

Approx. 10 mL urine (preferably morning mid-stream urine) will be collected.

For all biological samples collected, detailed instructions on sampling, preparation, processing, shipment and storage are provided in the laboratory manual. Plasma, serum and urine samples will be stored at an external biobanking facility contracted by the Sponsor; DNA, extracted from the original whole blood sample, will be stored at the Sponsor.

5.6 OTHER ASSESSMENTS

5.6.1 EQ-5D

Health related quality of life will be assessed using the EQ-5D-5L version (refer [Appendix 10.2.1](#)) according to the Flow Chart. EQ-5D is a standardised instrument for use as a measure of health outcome. It is designed for self-completion by patients.

The EQ-5D self-report questionnaire (EQ-5D) essentially consists of 2 pages comprising:

- the descriptive system (five dimensions of health; namely mobility, self-care, usual activities, pain/discomfort, anxiety/depression). Each dimension comprises five levels (no problems, slight problems, moderate problems, severe problems, extreme problems/unable to perform activity).
- the EQ-VAS (visual analogue scale) which records the patient's self-rated health status on a vertical graduated (0 – 100) VAS.

For further description on completing the questionnaire refer to the last part of [Section 5.2.1](#).

5.6.2 Health Care Resource Utilisation (HCRU)

HCRU data will be used for health economic analysis (i.e. cost-effectiveness analysis) required for reimbursement decisions. Resource use will be captured via interview with the patient and entered in the eCRF at all on-site visits during the complete trial period, and will allow calculation of direct and indirect costs. Main components to be collected are unscheduled outpatient visits and hospitalisations.

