Adverse events	X	X	X	X	X	X	X	X	X	X	X	X	X	X	X	X	X	X	5.3.7
KCCQ		X		X		X		X									X	X	5.2.1
EQ-5D		X		X		X		X				X				X	X	X	5.6.1
HCRU		X	X	X		X		X		X		X		X		X	X		5.6.2
Urine Pregnancy Test ¹³	X	X	X	X		X		X		X		X		X		X	X		5.3.4.2
Safety lab Tests	X ¹⁴	X	X	X		X		X		X		X		X		X	X	X	5.3.4
NT-proBNP	X	X	X	X				X				X					X	X	5.5
High-sensitivity TroponinT		X																	5.5
HbA1c ¹⁵	X	X		X		X		X		X		X		X		X	X		-

Trial Period	Screening ¹	Randomised Treatment Period ²															Follow Up Period ³		Relevant CTP section
		2	3	4	5 Phone call	6	7 Phone call	8	9 Phone call	10	11 Phone call	12	13 Phone call	14	15 Phone call	16	EOT Visit	FU Visit ³	
Visit	1																		
Trial week	-3	1	4	12	22	32	42	52	64	76	88	100	112	124	136	148	EOT Visit	EOT + 30 days	
Days from Randomisation Visit window ⁴	-28 to - 4	1	29±7	85 ±7	155 ±7	225 ±7	295 ±7	365 ±7	449 ±7	533 ±7	617 ±7	701 ±7	785 ±7	869 ±7	953 ±7	1037 ±7	---	---	
Fasting status ⁵	NF	F	NF	NF	-	NF		NF	-	NF	-	NF	-	NF	-	NF	F	F	
Lipid profile panel		X						X				X					X	X	5.3.4
eGFR (CKD-EPI _{cr} formula)	X	X	X	X		X		X		X		X		X		X	X	X	5.3.4.1
UACR	X	X	X	X		X		X		X		X		X		X	X	X	5.3.4
PK sampling (substudy) ¹⁶				X															5.4.1
Sampling for biobanking of serum/plasma/urine/ DNA (optional, requires separate informed consent) ¹⁷		X ¹⁸		X				X											5.5.1
Dispense trial medication ¹⁹		X	X	X		X		X		X		X		X		X			4.1.4 6.2.2
Return Medication/ medication compliance check			X	X		X		X		X		X		X		X	X		4.3

1. The screening procedures can be done on different days within the time window.
2. From Visit 8 and onwards, on-site visits will be scheduled every 24 weeks until end of trial.
Patients who prematurely discontinue trial medication will perform EOT visit and Follow Up visit, and then continue with scheduled visits until the trial is stopped.
For patients not willing to attend scheduled visits, telephone calls must be made regularly (ref. [Section 3.3.4.1](#)) to document any occurrence of outcome events and vital status.
If the trial continues beyond 148 weeks, visits are to be repeated with same intervals as from week 64 and onwards.
3. Timepoint for the EOT will be communicated via an Investigator letter when the Sponsor is confident that required number of events will be reached within a reasonable timeframe (ref. [Section 3.1](#) and [6.2.3](#)). All patients will have a follow up visit 30 days following regular or premature completion of the treatment period.

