3.3.4 Removal of patients from therapy or assessments

3.3.4.1 Removal of individual patients

This is a long-term outcome trial and every effort should be made by the site staff to encourage patients to remain in the trial and on trial medication unless medical condition substantially changes to alter the safety profile. If a patient is withdrawn from the trial the ExSC and the Sponsor should be informed immediately about each individual case.

Prematurely discontinuation of trial medication

For patients who prematurely discontinue trial medication all efforts should be made to observe these patients and ask them to continue to attend the scheduled visits until the end of trial. It is expected that all efforts are made to follow up on the collection of all adverse events, outcome events and concomitant therapy, and to have a complete dataset without missing data.

If a patient who prematurely discontinued trial medication is not willing to return to the predefined trial visits, at minimum a telephone call every 24 weeks (preferably every 12 weeks) and a telephone call at trial end will be required, to document the occurrence of outcome events and vital status. If possible, other AE's and concomitant therapy changes since last visit must be recorded.

Every attempt must be made by the Investigator to ensure patients continue participating in the trial during trial medication interruptions and after discontinuation of trial medication. Patients who prematurely discontinue trial medication are allowed to restart treatment, at any time if appropriate in the opinion of the Investigator. At every visit following trial medication discontinuation Investigators must consider if trial medication can be re-started.

Patients that are not actively taking trial medication may be less motivated to adhere to the scheduled trial visits. Investigators and site staff should work to detect early signs of losing interest and readily present such patients (not actively taking trial medication) with the following options to encourage continued participation:

- Option 1 Continue to attend regularly scheduled trial visits at the centre until the trial ends
- Option 2 Conduct all remaining trial visits over the phone

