- Change from baseline in KCCQ based on patient-preferred outcome at week 52
- Change in NYHA class from baseline at week 52
- Change from baseline in Health-related quality of life measured by EQ-5D
- Health economic analysis by Health Care Resource Utilisation
- Changes in NT-proBNP from baseline over time
- Change in albuminuria from baseline over time
- Change in albuminuria from baseline over time by baseline UACR) categories (<30 mg/g, ≥30mg/g to ≤300mg/g, >300 mg/g)
- Incidence of acute renal failure (based on narrow SMQ)
- Time to first acute kidney injury (based on the preferred term)
- Change from baseline in body weight over time
- Change from baseline in Systolic Blood Pressure (SBP) over time
- Change from baseline in Diastolic Blood Pressure (DBP) over time
- Change from baseline in pulse rate over time
- Change from baseline in HbA1c over time in the overall population and in 3 subgroups (non-DM, pre-DM, and DM)

Refer to the trial statistical analysis plan (TSAP) for the complete set of further endpoints.

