5.2.2 New York Heart Association classification

The New York Heart Association (NYHA) functional classification will be used to classify the severity of the patients' heart failure (ref. [Appendix 10.3](#)). The investigator should place the patients in one of the four categories based on how limited their physical activity are. Candidates for screening are required to have a NYHA functional class II, III or IV. The classification of patient's physical activity according to NYHA will be performed at all on-site until end of the trial. If a visit is designated as an on-site visit but is conducted by phone, the NYHA functional classification must be performed.

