5.6.2 Health Care Resource Utilisation (HCRU)

HCRU data will be used for health economic analysis (i.e. cost-effectiveness analysis) required for reimbursement decisions. Resource use will be captured via interview with the patient and entered in the eCRF at all on-site visits during the complete trial period, and will allow calculation of direct and indirect costs. Main components to be collected are unscheduled outpatient visits and hospitalisations.

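### The health care resource use interview is specified only for on-site visits, so unscheduled outpatient use is not collected after a patient who has stopped trial drug moves to phone visits

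*Protocol*

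**What the plan says.** Section 5.6.2 of the current protocol, unchanged from version 1.0, sets the timing: "Resource use will be captured via interview with the patient and entered in the eCRF at all on-site visits during the complete trial period". It names two items: "Main components to be collected are unscheduled outpatient visits and hospitalisations". It also gives the purpose: "HCRU data will be used for health economic analysis (i.e. cost-effectiveness analysis) required for reimbursement decisions". Section 5.1.3 lists "Health economic analysis by Health Care Resource Utilisation" among the further endpoints, outside the testing hierarchy of section 7.2.

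The Flow Chart marks HCRU at Visits 2, 3, 4, 6, 8, 10, 12, 14 and 16 and at EOT. It marks none of the phone calls and not the Follow Up Visit.

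For patients who stop trial drug, footnote 2 of the Flow Chart sets the default: "Patients who prematurely discontinue trial medication will perform EOT visit and Follow Up visit, and then continue with scheduled visits until the trial is stopped". Section 3.3.4.1 then gives four options for patients who may lose interest, among them "Option 2 Conduct all remaining trial visits over the phone". For those unwilling to attend, calls "will be required, to document the occurrence of outcome events and vital status", with other adverse events and concomitant therapy added where possible. Section 6.2.4 allows some assessments to be negotiated for reluctant patients, protecting only adverse events, outcome events and concomitant therapy.

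Section 5.2.2 has a rule for another assessment in the same situation: "If a visit is designated as an on-site visit but is conducted by phone, the NYHA functional classification must be performed".

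**The concern.** HCRU is an interview and can be done by phone, yet the schedule ties it to attendance. The patients offered phone visits are those who are not taking trial drug. Any resulting gap is therefore related to stopping treatment and cannot be treated as random.

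The item at risk is unscheduled outpatient visits, one of the two main HCRU components. At stake is the cost side of a cost-effectiveness analysis meant for reimbursement. Outpatient contacts that nobody asked about at the time are hard to recover later, so the remedy lies in data collection more than in analysis.

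**Working it through.** **Reading the sections together**

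1. Up to EOT: HCRU is marked at every on-site treatment visit and at EOT. A patient who stops drug early has an EOT visit, so use up to that point is recorded.
2. After EOT, default path: scheduled visits continue, on-site ones included, and HCRU continues with them.
3. After EOT, phone path (Option 2 of 3.3.4.1): neither 5.6.2 nor the Flow Chart provides for HCRU by phone. The calls described in 3.3.4.1 do not name it, and 6.2.4 does not protect it from negotiation. Outpatient use is not collected under any stated rule.
4. Hospitalisations on the phone path: these are still sought. Section 6.2.2 gives hospitalisations as an example of what phone contacts focus on, and outcome events must be documented under 3.3.4.1.

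The gap is therefore unscheduled outpatient visits, after the move to phone, in patients off drug.

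**Possible size**

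The protocol states no HCRU figure to reproduce. It gives no rate of stopping drug, no share moving to phone and no rate of outpatient use. The drop-out rate of under 1% per year in section 7.7 is drop-out from the trial, which is a different quantity. All inputs below are assumptions.

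- d, share stopping drug early: 10% to 25%
- p, share of those who move to phone: 20% to 50%
- move at mid-follow-up, so half of such a patient's time is missed
- k, outpatient use in the missed time relative to use elsewhere: 1.5 to 2

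Share of person-time without HCRU: s = d × p × 0.5

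- Low: 0.10 × 0.20 × 0.5 = 0.01, or 1%
- High: 0.25 × 0.50 × 0.5 = 0.0625, or about 6%

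Taking use elsewhere as 1, the true mean is (1 − s) + s × k = 1 + s(k − 1), while the mean per observed person-time is 1. The understatement is s(k − 1) / [1 + s(k − 1)].

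- Low: 0.01 × 0.5 / 1.005 = 0.5%
- High: 0.0625 × 1 / 1.0625 = 5.9%

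**Wider assumptions**, with d = 10% to 30%, p = 25% to 100%, k = 1.5 to 3 and the same mid-point move:

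- s runs from 0.10 × 0.25 × 0.5 = 1.25% to 0.30 × 1.00 × 0.5 = 15%
- understatement runs from 0.0125 × 0.5 / 1.00625 = 0.6% to 0.15 × 2 / 1.30 = 23%

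The upper end needs every patient who stops drug to go to phone, which runs against the protocol's default.

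**The case against.** The strongest reply is that the gap is inferred from silence. Option 2 moves the remaining visits to the phone and does not cancel them. Section 5.2.2 treats on-site as a designation that a visit keeps when it is held by phone, and 3.3.4.1 asks for a complete dataset. A site could reasonably ask the HCRU questions on such a call, and nothing forbids it. This stands in part: the text is open, not prohibitive. But 5.2.2 spells out the phone case for NYHA class and 5.6.2 does not, 6.2.4 lets HCRU be negotiated away, and sites may read the rule differently.

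It is also fair to say that short calls limited to outcome events and vital status help retain reluctant patients. That stands against adding HCRU to those minimum calls.

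Four stronger readings are tempting, and the protocol does not support them:

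- A reader might infer that patients who stop drug contribute no outpatient data, or that the cost data come mainly from adherent patients. HCRU runs through EOT, continued scheduled visits are the default, and no rate is given from which such a predominance could follow.
- A reader might infer that Amendment 1 repaired this gap for NYHA class and overlooked HCRU. Version 1.0 required NYHA at on-site and telephone visits alike. The amendment dropped the routine calls and kept visits designated as on-site, so it narrowed collection.
- The routine calls in 6.2.2 might be read as excluding outpatient use. They are said to focus on certain topics, and they fall between on-site visits for all patients, so they say little about Option 2.
- The missing HCRU mark at the Follow Up Visit might be read as a second gap. The Flow Chart and the list of examinations in 6.2.3 agree that HCRU is not done there. Only the word all in 5.6.2 is loose.

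**Conclusion.** The point holds as a limited gap in data collection. No rule provides for the HCRU interview once a patient off drug moves to phone visits. Followed as written, unscheduled outpatient use after the move is missing, and the missingness is related to stopping treatment.

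On the narrower assumptions about 1% to 6% of person-time lacks HCRU and mean outpatient use is understated by about 0.5% to 6%; the wider ones reach 23%. The protocol cannot settle which applies. The size rests on assumed stopping and switching rates, a move at mid-follow-up, heavier outpatient use after the move, and analysis per observed person-time. The difference between arms is affected only if stopping, moving to phone, or use after the move differs by arm, and nothing in the protocol allows that to be quantified.

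HCRU is a further endpoint, so no confirmatory result depends on it. This is a cheap improvement, not a defect that threatens the trial.

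**What to change.** Add one sentence to section 5.6.2, and a matching Flow Chart footnote on the HCRU row: when a visit designated as on-site is conducted by phone, the HCRU interview is also performed. This follows the form already used for NYHA class in 5.2.2.

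The existing eCRF page would need to be open for those contacts. The cost is a few more minutes on each such call, with no extra visit.

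Leave the minimum fallback calls for the least willing patients as they are. Adding questions there is a retention trade-off for the sponsor to weigh. If 5.6.2 is being edited anyway, its wording on all on-site visits can be aligned with the Flow Chart, which has no HCRU at the Follow Up Visit.
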